Laboratory Spirometry (SpiroLab)	X	X
Airway Inflammation (NIOX VERO)	X	X
Airway Reactivity (TremoFlo)	X	X
Cardiovascular Measures		
Vascular Reactivity (Vicorder or similar)	X	X
Blood Pressure	X	X
Heart Rate	X	X
Markers of endothelial dependent and independent function		
B-mode ultrasound (Vicorder or similar)	X	X
Arterial stiffness		
Pulse wave velocity and analysis (Vicorder or similar)	X	X

Evaluating E-Cigarette Nicotine Form, Concentration, and Flavors among Youth

E. Statistical Methods

Generalized linear mixed models will be employed to identify associations of nicotine form, nicotine concentration, and flavoring with various outcome measures (e.g., plasma nicotine, spirometry, flow-mediated dilation). Models will include relevant covariates (e.g., gender), a random effect for participant, main effects for nicotine form and concentration, and the interaction between nicotine form and concentration and nicotine form and flavor. Because of multiple measurements tested, we will assume a significance threshold corresponding to one expected false discovery per 100 tests ($p=0.01$).

i. Power Analysis

This study, for each of the main effects and $\alpha = 0.01$, achieves 80% power to detect an effect size of 0.5 standard deviations of the paired differences. For interaction effects, we will estimate 80% power (effect size 0.5 SD) to distinguish between any two of the interaction groups (e.g., free base/low nic, free base/high nic), while correcting for the pairwise tests ($p=0.01/6=0.0017$). Carryover and period effects will also be examined.

ii. Data Analytic Plan

Because product sampling will be randomized using a Latin Square, a fixed effect for session and a random effect for sequence will be included in all analyses.

iii. Missing Data

While we will make every effort to minimize the missing data for this study, missing data can arise due to various reasons. Violation of missing complete at random (MCAR) will be checked by evaluating whether any covariates are associated with missing data. If so, these covariates will be subsequently included and controlled for in the GLMM model. Our primary analysis will use mixed models which assumes Missing At Random (MAR) to deal with the missing data problem. In addition, sensitivity analyses will also be conducted using results from multiple imputation and complete cases strategies.

F. Gender/Minority/Pediatric Inclusion for Research

i. Inclusion of Women and Minorities

Inclusion of Women and Minorities: According to U.S. Census Data, 51.3% of Columbus, OH residents are female. In our previous studies with smokers, 55-62% of participants were female. According to U.S. Census data, the racial composition of individuals living in Columbus is 61% White, 28% Black or African American, 5% Asian, 0.2% American Indian/Alaska Native, 0% Native Hawaiian/Other Pacific Islander, and 4% two or more races. The ethnic composition of individuals living in Columbus is 6% Hispanic/Latino. We expect that our distributions will be similar to these but we may potentially have a larger distribution of ethnic and racial minorities, based on our previous studies. However, we will continuously monitor enrollment in order to ensure that we are meeting recruitment goals to avoid under-recruiting minorities. If the targeted enrollment for minorities is not met because they do not

Evaluating E-Cigarette Nicotine Form, Concentration, and Flavors among Youth

respond to the advertisements, we will make special efforts to solicit their participation by advertising in community newspapers, local church organizations, and community centers.

ii. Inclusion of Children

This study will be restricted to individuals 21 years of age and older, which is the legal age to purchase tobacco products.

G. Human Participants

i. Recruitment and Informed Consent

At first contact, all participants will be screened according to the study's inclusion/exclusion criteria. Those who are eligible will be given a brief verbal overview of the study and invited to participate. Informed consent (including a description of the nature, purpose, risks, and benefits of the study) of the participant will take place through both oral and written explanation of the study. The voluntary nature of the study and the participant's right to withdraw at any time will be stressed during the consent process. A copy of the informed consent will be provided to the participant in written form at the time of consent for them to keep. Informed consent will be collected by IRB approved study personnel. Recruitment script and materials, consent forms, and all study procedures will be approved by the OSU Institutional Review Board. All participants will provide written consent before any study data is collected.

ii. Potential Risks and Protections against Risk

There are minimal risks associated with this protocol. The protocol requires e-cig users 21 to 25 years of age to undergo 12 hours of tobacco/nicotine abstinence on nine occasions. These e-cig users will complete 9 vaping sessions – one session in which participants will use their own e-cig and e-liquid and subsequent sessions in which participants will use a study e-cig held at a constant wattage, and pre-filled with e-liquid of different nicotine form (free-base vs. nicotine salt), concentration (low-1% vs. high-5%), and flavoring (tobacco vs. menthol).

The participants are already using e-cigarettes and will only be asked to use or switch to what will be a fully characterized e-cigarette device and ITPs that have been fully described to FDA Center for tobacco products. Questionnaires, exhaled breath, and urine collection procedures are all non-invasive and involve minimal risk to study participants. Potential risks are as follows: a) risk of using e-cigarettes, b) loss of confidentiality or privacy, and c) risk of infection from blood draws.

1. Risk of Using ECs:

Risks

The risk of side effects and adverse events are very low. The commercial device we are using is sold online, and at e-cigarette specialty stores and convenience stores nationwide, without a prescription.

Protections

Evaluating E-Cigarette Nicotine Form, Concentration, and Flavors among Youth

Nevertheless, all participants will be screened for general medical precautions (pregnancy, cardiovascular disease) and monitored for adverse events during the study period. Study personnel will assess for adverse events via self-report at all follow-up visits. Any serious adverse events will be reported to the study's DSMB, and then to the OSU IRB and to the NIH. We will withdraw participants who have a serious adverse event, or become pregnant, begin to breastfeed, or have a cardiovascular or pulmonary event during the study. The most likely adverse (potential for nicotine overdose) event is anticipated to be rare (<5% in our team's previous studies) and mild (nausea, headache, disrupted sleep), and will be handled quickly (i.e., advice to participant to reduce or stop e-cig use). Lab studies of toxin exposure suggest that e-cigs incur no greater risk to health than do conventional cigarettes. Indeed, e-cigarettes generally show lower levels of harmful and potentially harmful constituents. To date, e-cigarette studies discussing adverse events report mild and tolerable side effects that generally resolved completely over time with continued use; the most predominant of which were mouth/throat irritation, cough, and headache. In four randomized clinical trials, no serious adverse events were reported, and the e-cigarette group and the nicotine patch group had comparable levels of adverse events in two studies. The most common were mouth irritation, throat irritation, dry cough and headache. Following the completion of the study, we will encourage all participants to quit their use of e-cigarettes.

2. Loss of Confidentiality and Privacy:

Risks

There is a risk of breach of confidentiality or a loss of privacy associated with taking part in the study.

Protections

Protection against loss of confidentiality and privacy will be maintained by numerically coding all data, disguising identifying information, and keeping data locked in file drawers or in a secure, password-protected database. Only study research assistants and the PI will have the information that connects participant's name and ID number. All electronic data will be numerically coded and stored in a password protected database, on a password protected computer in a secure research space. Participant information will be accessible only to research staff, who are pledged to confidentiality and complete training in the ethical conduct of research (i.e., both HIPAA and CITI trainings). Identifying information will not be reported in any publication.

3. Venous Draws:

Risks

The risks involved in drawing blood from a vein may include, but are not limited to, momentary discomfort at the site of the blood draw, possible bruising, redness, and swelling around the site, bleeding at the site, feeling of dizziness or lightheadedness when the blood is drawn, nausea, and rarely, an infection at the site of the blood draw.

Protections

Evaluating E-Cigarette Nicotine Form, Concentration, and Flavors among Youth

Blood will be drawn by trained research staff/research nurse. IVs will be placed by an RN or LPN. Sterile instruments will be used, and for blood draws, the participant's skin will be cleaned with an alcohol wipe at the site of the needle stick.

iii. Potential Benefits of the Proposed Research

Whereas no assurance can be made to an individual participant that s/he will personally benefit from this research, the experience should be beneficial. The immediate benefits of this research are scientific in nature, which in the long-term should benefit society as a whole. The study will also benefit e-cig users, as a group, by providing information as to the abuse liability of other e-cig/e-liquid products; and serve as evidence to inform regulatory action that improves public health. Overall, it is expected that the potential benefits to participants in the proposed study outweigh the potential risks.

H. Data and Safety Monitoring Plan and Board

i. Plan

Data will be analyzed initially after 20 participants are accrued, to ensure electronic data capture systems employed (i.e., REDCap) are accurately capturing data and to ensure the format and completeness of all data collected.

ii. Data and Safety Monitoring Board

The data and safety monitoring plan will involve the continuous evaluation of safety, data quality and data timeliness. Investigators will conduct continuous review of data and patient safety at their regular Disease Group meetings (at least monthly). The PI of the trial will review toxicities and responses of the trial where applicable at these disease center meetings and determine if the risk/benefit ratio of the trial changes. Frequency and severity of adverse events will be reviewed by the PI and compared to what is known about the agent/device from other sources; including published literature, scientific meetings and discussions with the sponsors, to determine if the trial should be terminated before completion. Serious adverse events and responses will also be reviewed by the OSUCCC Data and Safety Monitoring Committee (DSMC). The PI will also submit a progress report (biannually for Phase II and quarterly for Phase I) that will be reviewed by the committee per the IRB of record as per the policies of the IRB. All Serious Adverse Events are to be submitted to the DSMC for their review. Submissions are made via OnCore.

Adverse Events

Adverse events will be assessed by study staff at each visit via participant self-report and managed immediately. All adverse events will be reported to the OSU IRB. We will monitor for risk of smoking/vaping by screening participants for general medical precautions (pregnancy, cardiovascular disease). Any adverse events, breaks of confidentiality, or any other data or safety issues that arise will be discussed immediately between study personnel and [name]. [name] will be responsible for completing an Adverse Events Form should an event occur. [name] will report Serious Adverse

Evaluating E-Cigarette Nicotine Form, Concentration, and Flavors among Youth

Events to the OSU IRB within 24 hours of having received notice of the event. [name] will gather any information needed to investigate the event and to determine subsequent action. Any subsequent action will be documented and reported to the OSU IRB and the Program Officer at NIH. Adverse event reports will be reviewed annually with the OSU IRB to ensure participant safety.

Collection of Adverse Events

The collection of adverse events will be on a self-report basis and logged within an electronic data capture system (REDCap) or collected using standardized paper forms and will only be identified with the study ID of the participant.

I. Addendum

i. COVID-19 Related Procedures

Due to the COVID-19 pandemic, processes and procedures have been implemented to help protect participants and research staff. These processes and procedures are to be followed as long as social distancing requirements are necessary for conducting study visits.

Only one study participant per study coordinator will attend study visits at the CTR at any given time. All study participants will be provided with a face mask upon entry. Only one coordinator will meet the participant at their car for a temperature check, direct the participant into the building, and the two of them will ride the elevator to the 4th floor physically distanced at least 6 feet apart, both wearing masks. No more than 2 persons may ride the elevator at any given time. The participant will be immediately escorted to a private exam/draw room. Therefore, there will be no waiting in open lobby/waiting areas.

When in the exam room, the study coordinator will stand at least 6 feet away from the study participant to give instructions. Afterwards, the study coordinator will leave the exam room to allow the study participant to conduct the instructed procedures. The study coordinator and study participant will be at least 6 feet away from one another and wearing protective masks at all times during each visit.

Each study coordinator will have a designated exam/draw room and smoking room in which to conduct their designated research study. Each smoking room is separated from the staff control station in the hallway by its own door and contains a large window for the study coordinator to be able to see in and monitor study participant activity within the room. There is also a speaker and microphone system within each smoking room along with the Genetec software system on the outside of each room at the smoking room computer stations. Therefore, the study coordinator and study participant can communicate without being in the room together.

For study measures which cannot be physically distanced, appropriate PPE will be worn at all times by research staff during these procedures including goggles, face masks, gloves, and isolation gowns or lab coats.

After each participant visit is complete, there will be at least a 45-minute period for cleaning and air exchanges in the negative pressure rooms and for cleaning exam rooms and equipment before the next

Evaluating E-Cigarette Nicotine Form, Concentration, and Flavors among Youth

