While the long-term health effects of e-cigarettes are still unclear, studies examining proximal biomarkers of health indicate that e-cig users are exposed to many cardiovascular and pulmonary toxicants, including carcinogens, such as carbonyls, furans, reactive oxygen species, and heavy metals^{6,7}. Early evidence indicates that e-cig users experience adverse health effects, including increased oxidative stress, respiratory and mucosal inflammation, arterial stiffness and altered hemodynamics and platelet activity⁸. Moreover, use of nicotine by youth can adversely affect attention, learning, and memory, as well as lead to increased impulsivity. Taken together these data suggest that sustained e-cig use will likely have notable adverse health effects⁹. Since their introduction in 2015, to our knowledge, no studies have examined the toxicological and physiological effects of NSB device use, nor the impact of nicotine form. Previous research has largely focused on free-base nicotine devices, with only a few focusing on pulmonary and cardiovascular effects.

The youth vaping epidemic in the U.S. is drawing serious concern from parents, schools, health officials and regulators. There is now a wave of support and a need to create effective e-cig policies and regulations to prevent further proliferation of youth e-cig use. One of the most effective policies may be to create a product standard for nicotine to reduce the palatability and abuse liability of e-cigs for youth;

Evaluating E-Cigarette Nicotine Form, Concentration, and Flavors among Youth

however, strong scientific evidence is needed for the FDA to impose such regulations. The proposed project will begin to address this need.

A. Specific Aims

Utilizing a human laboratory design, we will examine the influence of nicotine form and concentration, and e-liquid flavor on youth vaping behavior, nicotine uptake, abuse liability, toxicant exposure, and acute cardiovascular and pulmonary effects. H1a: Nicotine salt (vs. free-base) and menthol flavored e-liquids (vs. tobacco flavored) will result in puffs of longer duration and higher flow rate, and a greater total inhaled aerosol volume, and H1b: demonstrate greater nicotine uptake, abuse liability, and adverse cardiovascular and pulmonary effects. H1c: High concentration, free-base nicotine (vs. salt nicotine) will result in puffs of shorter duration, lower flow rate, less volume, and lower abuse liability.

B. Significance

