Evaluating E-Cigarette Nicotine Form, Concentration, and Flavors among Youth

pH of aerosolized nicotine, resulted in greater and more rapid nicotine delivery—both known to be critical in the development of addiction^{14, 19}. Interestingly, tobacco industry documents also suggest that Phillip Morris in the race to increase levels of FB nicotine, had to course-correct and reduce the pH in a product that was too harsh and not acceptable to consumers¹⁶. As such, industry studies suggest that there is a trade-off between the level of FB nicotine and the harshness of the smoke^{20, 21}. The pH breakpoint where the smoke becomes noticeably harsh and undesirable to smokers was determined to be above 7.0¹⁷. Consequently, tobacco manufacturers continued to refine cigarettes to balance nicotine delivery with a “smooth” smoking experience²⁰. Today, cigarette smoke pH ranges from 6-7.8²², indicating that 4.5%-29% of the total nicotine is in FB form^{15, 23}.

Early E-cig models relied on e-liquid with higher pH levels and consequently high levels of FB nicotine. In one study, greater than 50% of all nicotine-containing e-liquids had a pH >9.0 and only 2 samples tested had a pH of <7.0²⁴. To account for this high pH level, and the harshness of FB nicotine, manufacturers had to lower the concentration of nicotine in their e-liquids (typically, 1.2-2.4% nicotine). However, these products were typically perceived to be less satisfying and palatable to smokers compared to combustible cigarettes²⁵. Moreover, as manufacturers began developing e-cig devices with significantly increased power (wattage) delivered to the heating coil (5- to 10-fold greater) in an effort to improve nicotine delivery²⁶, users began to accommodate the increased wattage by decreasing the concentration of their high pH e-liquid (0.3-0.6%) to reduce harshness²⁶. This strategy of high wattage and low nicotine concentration was successful in terms of improved nicotine delivery, but also had several unanticipated and negative effects²⁶. Increased power led to increased user exposure to tobacco toxicants due to greater production of carcinogenic compounds in the e-cig aerosol, and compensatory puffing, as users needed to take larger puffs to achieve satisfactory levels of nicotine delivery²⁶⁻³⁰.

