Utilizing a within-subjects, factorial design, 60 e-cig users (aged 21-25 years) will complete vaping sessions which will include a standardized, 5-minute, 10-puff vaping bout (30 seconds between each puff) followed by 30 minutes of ad libitum vaping. Prior to session one, participants will be asked to bring their own e-cig device and a full tank/pod to the first visit. In session one, participants will use their own e-cig and e-liquid. After visit 1, participants will take home a study e-cig device and 1 weighed pod pre-filled with study e-liquid (the participant was randomized to at the end of visit 1) to practice (20 puffs per day with the study device and until the participant feels comfortable) using the device before visit 2. Practice use with the study e-cig device and pre-filled pod will be verified based on data downloaded (via eScribe) from the device during visit 2. In the subsequent vape sessions, participants will use a study e-cig held at a constant wattage, and pre-filled with e-liquid of different nicotine form (free-base vs. nicotine salt), concentration (low-1% vs. high-5%), and flavoring (tobacco vs. menthol). There is no known commercial pair of nicotine liquids that differ only by nicotine form. For this study, we will prepare 8 e-liquids that differ by nicotine form, nicotine concentration, and flavor, simulating characteristics of popularly used nicotine liquids^{32,39}. E-liquids will be prepared from pure ($\geq 99\%$) S-(-)-nicotine; protonation and dilution of nicotine will be done using USP grade benzoic acid, and glycerol and propylene glycol, respectively. We will submit an Investigational Tobacco Product application to the U.S. FDA regarding the clinical use of the e-liquids. All sessions will be completed over nine visits for schedule Option A and 5 visits for schedule Option B. Study Schedule A consist of 9 separate visits and 9 separate vaping sessions. Study schedule B will consist of five separate visits (each visit will include up to 2 vaping sessions) each separated by a 3-hour washout period to allow nicotine levels to return to baseline. Each visit will be at least 48 hours apart. Participants will be required to report at least 12 hours abstinent from nicotine before each study visit. Participants will be told that their abstinence will be confirmed at the time of visit via blood plasma nicotine analysis. This is a partial bogus pipeline⁴⁰; 3mL venous blood sample will be collected for later analysis.; those with plasma nicotine levels $>3\text{ng/mL}$ at the time of their visit will be replaced post hoc with another participant. We conservatively estimate replacing 10% of participants. Measures of topography, nicotine uptake, abuse liability, subjective effects, and cardiovascular and pulmonary effects will be collected (see Table 1). Exposure to select toxicants, including nicotine and menthol in total particulate matter, and gas phase carbonyls and volatile organic compounds, will also be estimated post hoc using puff playback machine smoking.

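### The Section E model forces one menthol effect for 1% and 5% within each nicotine form, so the eight crossed liquids cannot show whether flavor acts differently by strength

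*Combined protocol and SAP*

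**What the plan says.** Section D.ii (Study Procedures) sets out the design: "Utilizing a within-subjects, factorial design, 60 e-cig users (aged 21-25 years) will complete vaping sessions". The liquids are the full set of two forms (free-base, salt), two concentrations (1%, 5%) and two flavors (tobacco, menthol): "For this study, we will prepare 8 e-liquids that differ by nicotine form, nicotine concentration, and flavor". Each participant is meant to use all eight.

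Section A (Specific Aims) gives the purpose: "we will examine the influence of nicotine form and concentration, and e-liquid flavor on youth vaping behavior". H1a and H1b compare menthol with tobacco overall. H1c compares free-base with salt at high concentration and does not mention flavor.

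Section E lists these treatment terms: "main effects for nicotine form and concentration, and the interaction between nicotine form and concentration and nicotine form and flavor". Section E.ii adds that "a fixed effect for session and a random effect for sequence will be included in all analyses". A participant random effect and covariates complete the model. Nowhere is a concentration-by-flavor term or a three-way term listed, and a flavor main effect is not listed either. Section E.i corrects pairwise comparisons by 0.01/6, which fits the four groups of a two-way table.

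**The concern.** The treatment structure has eight cells, and the model has too few terms to fit eight means. What is left out is any dependence of the flavor effect on nicotine strength within a form. The plan intends its results to inform a nicotine product standard. For that purpose, whether menthol changes the response to a 5% free-base liquid is a different question from whether menthol matters on average over 1% and 5%. The data will contain the answer to both, but the planned model can give only the second.

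There is also a robustness issue. When a factorial model omits terms that are not zero, its averaged contrasts are safe only while the cells stay balanced. An unpleasant liquid is a plausible place for sessions to go missing.

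**Working it through.** **The plan's own figures.** Section E.i states 80% power for 0.5 SD of the paired differences at alpha 0.01. With n = 60 and a two-sided paired t test (sidedness is not stated, so this is assumed), the power is 88%, and 80% needs 51 participants. The stated 80% is therefore not reproduced at 60, but it errs on the cautious side. The correction reproduces: 0.01/6 = 0.0017. Nothing below rests on the 80%.

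**Parameter count.** Within one form the listed terms give an additive model: intercept + concentration + flavor. That is 3 parameters per form, so 6 for 8 liquids. The count is 6 whether form-by-flavor is fitted as a factor term or a flavor main effect is added explicitly. If form-by-flavor were entered as a single product column with no flavor main effect, the count would be 5 and the flavor estimate would depend on coding. The equality across strengths holds in every case. Session, sequence, participant and covariates do not separate the liquids further.

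**Illustration (an assumption, not from the documents).** Only free-base 5% tobacco differs, by -D. With balanced data and an identity link, the additive fit is row mean + column mean - grand mean. In units of D, the free-base row means are -0.5 (5%) and 0 (1%), the column means are -0.5 (tobacco) and 0 (menthol), and the grand mean is -0.25.

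| Free-base liquid | True | Fitted |
|---|---|---|
| 5% tobacco | -1 | -0.5 - 0.5 + 0.25 = -0.75 |
| 5% menthol | 0 | -0.5 + 0 + 0.25 = -0.25 |
| 1% tobacco | 0 | 0 - 0.5 + 0.25 = -0.25 |
| 1% menthol | 0 | 0 + 0 + 0.25 = +0.25 |

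All salt cells are fitted as 0.

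- Menthol minus tobacco in free-base: true D at 5% and 0 at 1%; fitted 0.5D at both. The average, 0.5D, is correct.
- H1c (free-base minus salt at 5%): true (-1 + 0)/2 = -0.50D; fitted (-0.75 - 0.25)/2 = -0.50D. It is unchanged.
- A generalized least squares fit on an 8x8 Latin square, with session fixed and participant and sequence random, gives the same 0.5D and 0.5D.
- Milder case: if the 1% effect is half the 5% effect, the model reports 0.75 of the 5% effect at both strengths.

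**Missing sessions.** Suppose 30% of the free-base 5% tobacco sessions (18 of 60) are missing at random under the same pattern. The planned model's H1c contrast moves from -0.50D to -0.45D. The eight-mean model stays at -0.50D.

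**Are both missing terms needed?** With concentration-by-flavor alone (7 parameters), the fitted menthol effects are 0.25D (1%) and 0.75D (5%) in free-base, and -0.25D and +0.25D in salt, where the truth is 0. With the three-way term as well (8 parameters), the fit is exact.

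**Power for the omitted contrast.** Take a residual SD of 1 per session. The difference between the 5% and 1% menthol effects in free-base uses four sessions, so its SD per participant is sqrt(4) = 2 and the standardised effect is D/2. The plan's 0.5 SD of a paired difference, applied to two single sessions, means D = 0.5 x sqrt(2) = 0.71. With n = 60, two-sided, at 0.01:

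| D (residual SD) | 0.5 | 0.71 | 0.75 | 1 |
|---|---|---|---|---|
| Power | 24% | 53% | 60% | 88% |

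**Precision.** The standard error of the menthol effect pooled over strengths within a form is sqrt(1/60) = 0.129. At a single strength it is sqrt(2/60) = 0.183, larger by sqrt(2).

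**The case against.** The strongest defence is that the model matches the hypotheses. H1a and H1b state the menthol effect overall, H1c concerns form at high concentration, and none says that the flavor effect depends on strength. A form-by-flavor result is by construction an average over strengths, and that average is estimated correctly. This stands. A reader might infer that the planned hypothesis tests are biased, but with balanced data they are not.

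A reader might also infer that the plan's own rationale predicts a menthol effect confined to 5% free-base. Section B.2 does say of free-base liquids: "To account for this high pH level, and the harshness of FB nicotine, manufacturers had to lower the concentration of nicotine in their e-liquids". That concerns form and concentration, which the model already lets interact. Nothing in the documents says that menthol masks free-base harshness. The same section also describes highly flavored, low-nicotine starter products, which would make flavor matter at low strength. The one-cell pattern is therefore only an illustration.

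Nor do the documents say that a pooled flavor result will be claimed at each strength. The liquid-by-liquid toxicant work uses observed puffing averaged per liquid, not this model, so it is untouched.

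Finally, a reader might set 71% power at 0.0017 for the pooled free-base menthol effect (D = 1) against 88% at 0.01 for the omitted contrast, and read the gap as a difference between the two tests. Both have standardised effect D/2, so the gap comes only from the two alphas.

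What the defence does not answer is that the constancy of the flavor effect over strength is imposed without being stated or checked, although the design can check it.

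**Conclusion.** The point holds as a limit on what the analysis can say, not as an error in a stated test. Within each form the model fixes one menthol effect for 1% and 5%, on the link scale. The menthol effect may still differ between free-base and salt. In the illustrative extreme, half of a 5%-only effect is reported at each strength; less extreme patterns distort less.

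The halving assumes balanced data and an identity link. The correctness of the within-form average also assumes that a flavor main effect is included or understood, which Section E should say. The averaged contrasts can shift if missing sessions gather in one liquid: about 0.05D for H1c in the case shown.

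Power to detect strength dependence is moderate, about 53% at an effect matched to the plan's 0.5 SD. That argues for estimates with intervals rather than reliance on a test. It does not argue for setting the term to zero. This is a worthwhile, inexpensive improvement.

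**What to change.** In Section E:

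- Write in the flavor main effect, and add the concentration-by-flavor and form-by-concentration-by-flavor terms, so that all eight liquid means are fitted.
- Keep the H1a-H1c contrasts as equally weighted marginal averages from this model.
- Always report menthol versus tobacco at 1% and at 5% within each form, with confidence intervals, and not only after a significant interaction test. Label these comparisons secondary or exploratory and outside the 0.01/6 correction.

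The cost is SAP wording and two more terms per outcome. The two fixed-effect degrees of freedom are small beside 60 participants with eight study-liquid sessions each, and in the balanced design the added terms leave the planned contrasts' estimates unchanged. The strength-specific effects are less precise than the pooled one (standard error larger by sqrt(2)), but they are reported in addition to it. No extra visits or participants are needed.
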